5.2.4 Biomarkers

The following biomarkers will be collected:

- ALT
- AST
- caspase 3/7
- cCK18/M30
- fICK18/M65
- Enhanced Liver Fibrosis (ELF) score (based on hyaluronic acid, P3NP, TIMP-1)

The change from baseline will be derived for each of these biomarkers. If any biomarker variables are not normally distributed, a log-transformation may be applied to that biomarker endpoint prior to analysis.

5.2.5 Liver Stiffness

Liver stiffness will be assessed by transient elastography (FibroScan®) performed at seven sites on a subset of the entire study population. Fibroscan® is collected at screening and Months 6, 12, 18, and 24. Only values meeting the specific success criteria (interquartile range [IQR] / median liver stiffness <30% and success rate >60%) will be summarized. The change from baseline in liver stiffness will be derived using all available data.

5.3 EXPLORATORY ENDPOINT

A morphometric assessment will be made on all biopsies collected at screening and Months 12 and 24. Effects on liver collagen and smooth muscle actin (SMA) will be assessed by

morphometric image analysis. The change from baseline in percent of liver collagen and SMA will be derived.

5.4 SAFETY ENDPOINTS

5.4.1 Treatment Compliance

Study drug dispensation information and treatment compliance data will be collected throughout the study. The number of capsules dispensed, number of capsules returned, number of missed doses and study drug interruptions data will be collected. Treatment compliance will be calculated in the database and is defined as: (the number of capsules dispensed minus the number of capsules returned) divided by the number of expected doses.

5.4.2 Extent of Exposure

Overall treatment exposure will be derived as the number of days from the first date of study drug administration to the last date of study drug administration (inclusive of the first and last dates of dosing), regardless of study drug interruptions. Person years of exposure will be derived as the overall exposure divided by the number of person years observed, where 1 year is equal to 365.25 days.

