3 STUDY DETAILS

3.1 STUDY DESIGN

This is a double-blind, randomized, multicenter study involving subjects with chronic HCV who underwent liver transplantation; developed HCV-related liver fibrosis or cirrhosis; achieved SVR following anti-HCV therapy; and still show demonstrable fibrosis or cirrhosis on liver biopsy. Upon successful screening, subjects are randomized to receive 25 mg BID of emricasan or placebo in a 2:1 ratio.

The subjects are stratified based on the stage of fibrosis or cirrhosis at Baseline:

- Ishak F2
- Ishak F3-F5
- Ishak F6

The duration of each subject's participation will be approximately 26.5 months and will consist of:

- Screening period of up to 6 weeks
- Double-blind treatment period of 24 months
- A follow-up visit 4 weeks after completion of treatment

The schedule of events is provided in [Appendix 1](#) of the protocol.

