3.3 RANDOMIZATION

The assignment to emricasan or placebo will be performed randomly in a 2:1 ratio to emricasan 25 mg BID or matching placebo BID. Approximately 60 subjects will be enrolled in this trial with 40 assigned to emricasan and 20 assigned to placebo. Randomization will be stratified based on baseline Ishak Fibrosis Score: F2, F3-F5, or F6.

The randomization schedule will be generated using a validated randomization program and verified for accuracy using strict quality control procedures. Randomization numbers and study drug assignment will be centrally coordinated through the study's Interactive Web Randomization System (IWRS).

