11.1 DOSING AND EXTENT OF EXPOSURE

Study drug capsule counts will be summarized descriptively by treatment group and visit. Treatment compliance and extent of treatment exposure endpoints (i.e., days and person years of exposure) will be summarized descriptively by treatment group.

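### The SAP's person-years formula is circular and does not return person-years; the effect is limited to one descriptive exposure summary

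*SAP*

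**What the plan says.** SAP 5.4.2 gives two linked definitions. The first fixes the unit and the span: "Overall treatment exposure will be derived as the number of days from the first date of study drug administration to the last date of study" (the quote stops just short of the end of the phrase; the span closes at the last dose). Both end dates count, and interruptions are ignored. The second builds on it: "Person years of exposure will be derived as the overall exposure divided by the number of person years observed", followed in the same sentence by "where 1 year is equal to 365.25 days". The SAP does not define person-years observed anywhere else.

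The result goes into a planned output. Under SAP 11.1, "Treatment compliance and extent of treatment exposure endpoints (i.e., days and person years of exposure) will be summarized descriptively by treatment group". That section neither restates nor corrects the formula.

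The time spans and arm sizes needed for a worked example are in SAP 3.1 ("Double-blind treatment period of 24 months" and "A follow-up visit 4 weeks after completion of treatment") and SAP 3.3 ("Approximately 60 subjects will be enrolled in this trial with 40 assigned to emricasan and 20 assigned to placebo").

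**The concern.** The numerator is a count of days and the divisor is in person-years, so the quotient is in days per person-year. To convert days to years, the divisor should be the number of days in a year. The written rule instead divides by person-years, the quantity that the sentence sets out to define.

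The SAP is the specification against which programming and independent checking are done. Code that follows the sentence gives a number that is not person-years. Code that gives person-years departs from the sentence. On the most direct reading, the per-subject value would also be the same constant in both arms, so this part of the summary would hide any difference in time on drug.

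**Working it through.** The documents state no person-years figure to reproduce, so the check applies the formula to example subjects.

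**Inputs**
- Exposure D, in days, from first to last dose inclusive (SAP 5.4.2).
- 365.25 days per year (SAP 5.4.2).
- Treatment period of 24 months (SAP 3.1), taken here as 731 days inclusive. The day count is an assumption.
- Follow-up visit four weeks, or 28 days, after treatment ends (SAP 3.1).
- 40 emricasan and 20 placebo subjects (SAP 3.3). All are assumed to complete, for the group totals only.

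**Formulas**
- Conversion using the SAP's own constant: D / 365.25.
- Reading A: person-years observed covers the first-to-last-dose span, the only span that SAP 5.4.2 defines. Then D / (D / 365.25) = 365.25 for any D.
- Reading B: person-years observed is exposure plus 28 days. Then D / ((D + 28) / 365.25).
- Reading C: person-years observed is the full 24 months plus 28 days for every subject. Then D / (759 / 365.25), since 731 + 28 = 759.

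| Exposure D (days) | D / 365.25 | Reading A | Reading B | Reading C |
|---|---|---|---|---|
| 14 | 0.038 | 365.25 | 121.8 | 6.7 |
| 183 | 0.501 | 365.25 | 316.8 | 88.1 |
| 365 | 0.999 | 365.25 | 339.2 | 175.6 |
| 731 | 2.001 | 365.25 | 351.8 | 351.8 |

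The last row in full: 731 / 365.25 = 2.001. Under A, 731 / 2.001 = 365.25 (unrounded divisor). Under B and C, 759 / 365.25 = 2.078 and 731 / 2.078 = 351.8.

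**Group totals if all complete**
- Conversion: 40 × 731 / 365.25 = 80.1 person-years on emricasan and 20 × 731 / 365.25 = 40.0 on placebo.
- Reading A, summed over subjects: 40 × 365.25 = 14,610 and 20 × 365.25 = 7,305. Each is about 182.5 times the converted total (365.25 / 2.001).
- Reading A, applied once to the pooled days of an arm: 365.25 in either arm.

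None of the three readings returns person-years.

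**The case against.** The strongest reply is that the sentence carries its own correction. It ends by setting a year at 365.25 days, so the right constant is present and the likely intent is days divided by 365.25. Under reading A, a programmer would have to compute the correct value first and then divide the days by it. The result would be 365.25 for everyone in a two-year trial, beside a correct column of days, and would probably be noticed. All of this stands, and it lowers the severity. It does not repair the rule, because the clause supplies a conversion and leaves the stated divisor as it was.

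Three stronger inferences are tempting, and the documents do not support them.

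- **Every subject necessarily gets about 365, an inflation of about 180-fold.** This holds only under reading A. Person-years observed is undefined, and readings B and C give other values, with lower ones for early discontinuers.
- **Exposure-adjusted adverse event rates would be meaningless.** Such a rate appears only in the SAP's abbreviation list. SAP 11.2 itemises the adverse event summaries as incidences, and none is adjusted for exposure. No planned rate uses this quantity as a denominator.
- **The whole exposure table is wrong.** Exposure in days is properly defined and reported alongside. Only the person-years entries are at risk.

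It is also fair to say that a treatment-group total is a reporting choice. SAP 11.1 asks for descriptive summaries, which subject-level values satisfy, so only the divisor has to change.

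**Conclusion.** The formula is wrong as written and nothing else in the SAP corrects it. It is circular, and its result is in days per person-year.

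The size depends on an undefined term. With person-years observed taken as exposure divided by 365.25, every subject gets 365.25, against about 2.0 for a 24-month completer. With off-drug follow-up included, a completer gets about 352. Both completer figures assume 731 days of treatment, and the second also assumes 28 days of follow-up.

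The reach is small: the person-years part of one descriptive safety summary. Exposure in days, the planned adverse event tables, the primary endpoint and the three-category decision guideline do not depend on it. This is a minor point, probably a drafting slip, and worth correcting because the quantity is a planned output.

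**What to change.** Replace the second sentence of SAP 5.4.2 with: *Person-years of exposure = overall treatment exposure (days) / 365.25.* If a treatment-group total is shown, state that it is the sum of the subject values.

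The change costs one sentence. It keeps the SAP's own constant, needs no new data or analysis, and leaves SAP 11.1 as it stands.

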5.4.3 Adverse Events (AEs)

Adverse events will be collected during the study and will be coded using the Medical Dictionary for Regulatory Activities (MedDRA). All events with a start date on or after the first date of study drug administration to the last study visit date are defined as treatment-emergent adverse events (TEAEs).

Adverse events classified as definitely, probably, and possibly related to study drug will be summarized together as related AEs. Adverse events classified as unlikely and not related will be summarized together as not related AEs. For summary purposes, the AE relationship will be summarized as related, not related, or unknown.

5.4.4 Liver Ultrasound

Liver ultrasounds are performed at Screening, Month 6, Month 12, Month 18, and Month 24. Ultrasound data will be reviewed for evidence of any new focal hepatic lesion as well as for any evidence of new gallbladder inflammation.

5.4.5 Liver Monitoring

Liver transaminases (ALT, AST) and total bilirubin will be monitored at each study visit during the study for any evidence of potential DILI. The following categories for ALT, AST, and total bilirubin will be derived:

- Maximum post-baseline comparison to upper limit of the normal range (ULN):
 - ALT
 - \leq ULN
 - $>$ ULN and $\leq 3 \times$ ULN
 - $>3 \times$ ULN and $\leq 5 \times$ ULN
 - $>5 \times$ ULN and $\leq 8 \times$ ULN
 - $>8 \times$ ULN

- AST
 - \leq ULN
 - $>$ ULN and $\leq 3 \times$ ULN
 - $>3 \times$ ULN and $\leq 5 \times$ ULN
 - $>5 \times$ ULN and $\leq 8 \times$ ULN
 - $>8 \times$ ULN
- Total bilirubin
 - \leq ULN
 - $>$ ULN and $\leq 1.5 \times$ ULN
 - $>1.5 \times$ ULN and $\leq 2 \times$ ULN
 - $>2 \times$ ULN and $\leq 3 \times$ ULN
 - $>3 \times$ ULN
- Maximum post-baseline value $>2 \times$ baseline
- Maximum post-baseline value $>3 \times$ baseline
- Elevated post-baseline ALT and/or AST with concurrent (i.e., same post-baseline visit) elevated total bilirubin
 - ALT $>3 \times$ ULN and concurrent total bilirubin $>2 \times$ ULN
 - AST $>3 \times$ ULN and concurrent total bilirubin $>2 \times$ ULN
 - Either ALT or AST $>3 \times$ ULN and concurrent total bilirubin $>2 \times$ ULN
 - Both ALT and AST $>3 \times$ ULN and concurrent total bilirubin $>2 \times$ ULN
- Elevated Post-baseline ALT and/or AST with elevated total bilirubin (not necessarily concurrent)
 - ALT $>3 \times$ ULN and not necessarily concurrent (i.e., across all post-baseline visits) total bilirubin $>2 \times$ ULN
 - AST $>3 \times$ ULN and not necessarily concurrent total bilirubin $>2 \times$ ULN
 - Either ALT or AST $>3 \times$ ULN and not necessarily concurrent total bilirubin $>2 \times$ ULN
 - Both ALT and AST $>3 \times$ ULN and not necessarily concurrent total bilirubin $>2 \times$ ULN

5.4.6 Laboratory Measurements

Laboratory tests include measurements across panels of hematology, coagulation, chemistry, and urinalysis. In addition, alpha-fetoprotein is measured at screening and every 6 months during the study. All specific laboratory tests are listed in detail in clinical protocol [IDN-6556-07](#). Normal ranges, where applicable, will be provided by the central laboratory and used to identify laboratory measurements outside the normal range.

Changes from baseline will be derived for each continuous laboratory parameter. Laboratory tests with categorical results will have no derivations made.

5.4.7 Vital Signs, Weight, and Height

Vital signs include systolic blood pressure, diastolic blood pressure, heart rate, respiratory rate, and temperature. Body weight and height will be collected at protocol specified visits (weight at

screening, Month 12, and Month 24, height at screening only), and body mass index (BMI) will be derived as [weight in kilograms] / [height in meters²].

Changes from baseline in vital signs, weight, and BMI will be derived.

5.4.8 Electrocardiograms

Electrocardiogram (ECG) data to be reported includes ventricular rate, PR interval, RR interval, QRS interval, QT interval, QTc interval, QTcB interval, QTcF interval, and findings (i.e., normal or abnormal). Post-dose maximum values in QTcB and QTcF will be classified into the following categories, in milliseconds (ms):

- <450
- ≥450 to <480
- ≥480 to <500
- ≥500

Changes from baseline in PR interval, QRS interval, QT interval, QTc interval, QTcB interval, and QTcF interval will be derived at each respective visit. Changes from baseline values in QTcB and QTcF will be classified into the following categories, in ms:

- <30
- ≥30 to <60
- ≥60

5.4.9 Medications

All additional medications taken any time during the study will be recorded at each study visit. Medications will be classified into 1 of the following 3 types:

- Prior Medication: any medication stopped prior to the first date of study drug administration
- Concomitant Medication: any medication started prior to and stopped on or after the first date of study drug administration
- New Concomitant Medication: any medication started on or after the first date of study drug administration

All medications will be coded using the world health organization drug dictionary.

Immunosuppressant therapy relative to a subject's liver transplant is collected at screening and will be classified as tacrolimus, cyclosporine, or other.

Previous hepatic treatments were collected at screening. These medications will be manually reviewed and classified as anti-viral, immunotherapy, and anti-viral+immunotherapy. These medications will also be classified as interferon-based or not.

5.4.10 Physical Examination

A comprehensive physical examination will be performed and will include assessments of general appearance, skin, head, eyes, ears, nose, throat, neck (including thyroid), lymph nodes, chest, heart, abdomen (including liver and spleen examination), extremities, and nervous system. No derivations will be made for physical examination components results.

6 ANALYSIS POPULATIONS

The Enrolled Set (ES) is defined as the set of subjects who provide a signed informed consent form to participate in this study.

The Full Analysis Set (FAS) consists of all randomized subjects who have received at least one dose of study drug. If the administration of study drug is not certain, the subject will be allocated to the FAS. The FAS is representative of the intention-to-treat principle assigning subjects to the planned randomized study drug assignment and will be analyzed as randomized.

The Per-Protocol Set (PPS) is defined as the set of subjects included in the FAS who have no significant protocol deviations that impact the primary endpoint and who provide a Month 24 liver biopsy. The PPS will be defined during a blinded data review meeting prior to database lock based on considerations like major protocol deviations affecting the primary endpoint, inadequate study drug compliance, etc. Meeting minutes and the final deviation tracker will serve as documentation for classification of subjects into the PPS.

The Safety Analysis Set consists of all subjects who are randomized and receive at least one dose of study drug. Subjects will be analyzed on an “as treated” basis (i.e., all subjects will be analyzed by the treatment they actually received). If no errors in randomization assignments occur, then the FAS and Safety Analysis Set will be the same.

7 GENERAL STATISTICAL CONSIDERATIONS

All biopsy data analyzed by and collected from the central histopathologist will be used in the FAS for all efficacy analyses, unless stated otherwise. All biopsy data collected per local assessments will be captured in the database and will be provided in a listing by visit.

Analyses will be conducted using SASv9.3 or higher and pooled across all enrolling sites. Data will be summarized descriptively with categorical variables being summarized using number of observations and percentages; continuous variables being summarized by n, mean, median, standard deviation, minimum, and maximum, unless otherwise specified.

All disposition, demographics, and baseline summaries will be based on using the FAS, with the disposition table also being summarized using the ES. The efficacy analyses will be based on the FAS, with the primary analysis also performed on the PPS. All safety analyses will be based on the Safety Analysis Set.

All summaries by treatment group will include each of the planned two treatment groups and all subjects combined (i.e., total).

All subjects will be assigned a unique subject number, which will consist of the study site identification concatenated with the assigned subject number.

For purposes of laboratory summaries, baseline is defined as an average all values observed up to and including Day 1. For purposes of abnormality laboratory summaries and all other analyses, baseline is defined as the last observed value up to and including Day 1.

Formatting of numerical results will include the following:

- Mean values will be reported to 1 decimal place more than the data collected.
- Standard deviation values will be reported to 2 decimal places more than the data collected.
- Median, minimum, and maximum values will be reported to the same decimal place as the data collected.
- Percentages will be reported to 1 decimal place.
- Where confidence intervals (CI) are to be reported, CIs for means will be reported to the same decimal places as mean values; CIs for percentages will be reported to 1 decimal place.
- All p-values will be reported to 3 decimal places.

8 SUMMARY OF STUDY POPULATION DATA

All study population data will be provided in subject specific listings. The disposition table will be produced using the ES and FAS. All other study population data tables will be produced using the FAS.

8.1 SUBJECT DISPOSITION

Subject disposition will be summarized descriptively by treatment group. The disposition summary will include results for subjects enrolled, subjects randomized, subjects treated, subjects included in each analysis population, discontinuation of study drug, reason for study drug discontinuation, study completion status, and reason for study withdrawal.

8.2 PROTOCOL DEVIATIONS

Protocol deviations will include the deviation recorded, the deviation category, and significance classification. The deviation category refers to the general aspect of the study the deviation affects. Classifications of protocol deviations will be determined by the clinical trial study team prior to database lock during a blinded data review meeting.

Protocol deviations will be summarized descriptively by treatment group. A listing of protocol deviations by unique subject number will be provided.

Reasons for screen failure will also be summarized by treatment group.

8.3 DEMOGRAPHICS

Subject demographics will be summarized descriptively by treatment group. The demographics summary will include results for subject age, age group, gender, race, and ethnic category. Age group is defined as the following categories:

- 18 - 40 years
- ≥ 40 - 64 years
- > 64 years

8.4 BASELINE CHARACTERISTICS

Baseline characteristics include the following:

- Ishak fibrosis score
- Knodell histological activity index components (interface hepatitis, confluent necrosis, parenchymal injury, and portal inflammation)
- Liver collagen and SMA
- biomarkers (ALT, AST, caspase 3/7, cCK18/M30, and fCK18/M65)
- Laboratory Parameters (platelet count, total bilirubin, albumin, INR)
- Weight, BMI

The number and percentage of patients who are receiving either tacrolimus or cyclosporin as their immunosuppressant medication at the time of randomization, as well as the type of previous hepatic treatment received, will be included as part of the baseline characteristics.

All baseline characteristics will be summarized descriptively by treatment group. A listing of baseline characteristics will be provided by unique subject number.

8.5 TRANSPLANT AND HCV HISTORY

Transplant and HCV history will be summarized by treatment group. The transplant history summary will include:

- Number of years since transplant
- Liver donor age
- HCV positive donor Liver
 - Yes
 - No
- Source of transplant
 - Living
 - Cadaveric
- Immunosuppression regimen
 - Tacrolimus
 - Cyclosporine
 - Other
- Time since SVR (calculated as 12 weeks post end of previous hepatic treatment date treatment date)
- Previous HCV treatment post-transplant
 - Treatment Type
 - Antiviral
 - Immunotherapy
 - Antiviral+Immunotherapy
 - Interferon Based Treatment
 - Yes
 - No

9 EFFICACY ANALYSES

All primary, secondary, and exploratory endpoints will be summarized descriptively by treatment group at each study visit, using the FAS. Also, a sensitivity analysis for the primary endpoint will be produced using the PPS. The individual components of the primary endpoint will also be summarized descriptively by treatment group at each study visit.

All efficacy endpoints will be provided in listings by unique subject number and visit.

9.1 PRIMARY EFFICACY ANALYSIS

All screening and post-baseline biopsy data collected will be used in the primary analysis, irrespective of the defined protocol visit window. Classification of the Ishak fibrosis score will be summarized descriptively by treatment group at baseline, Month 12, and Month 24. Response at Months 12 and 24 will be summarized descriptively by treatment group, along with exact (Clopper-Pearson) 95% confidence intervals (CIs). The risk difference between groups will also be provided with its 95% CI.

For the primary efficacy analysis based on the Month 24 biopsy, subjects with a missing Month 24 biopsy will have their Ishak fibrosis score imputed. Imputation of missing Ishak fibrosis scores will be conducted using multiple imputation (MI). Results will be imputed based on age, gender, baseline Ishak fibrosis score, and the Month 12 Ishak fibrosis score. Imputations will be based on at least 5 imputed datasets, depending on the percent of missing observations and will be documented in the clinical study report. Within each imputed dataset, the change from baseline at Month 24 will be derived to allow categorization into response or no response as defined in [Section 5.1](#).

Study success will be determined per the criteria described in [Section 0](#). This primary analysis will be conducted using the FAS.

The following sensitivity analyses will be provided for the primary efficacy endpoint, using different methods for the handling of missing liver biopsy results at Month 24:

- All FAS observed post-baseline biopsies
- All FAS observed post-baseline at Month 24 (within the sensitivity analysis visit window, per [Section 3.5](#))
- FAS with missing M24 biopsy imputed to ‘No’ response
- Per-protocol

Response rates at Month 12 will be summarized using the FAS in the same manner as the response rates at Month 24 (i.e., using MI). Subjects with a missing Month 12 liver biopsy will have their Month 12 Ishak fibrosis score imputed based on age, gender, and baseline Ishak fibrosis score.

